# 7.3.13.4. Time from clinically significant disease reactivation to return to pre-flare steroid dose.

**Endpoint:** See Section 7.2.1, *Computation of the Primary Endpoint*, for details on the definition of clinically significant SLE reactivation. Medications, including steroid use, are assessed at each study visit throughout the duration of the study and are collected on the *Prior/Concomitant Medications* CRF page.

For each subject who experiences disease reactivation, time from clinically significant disease reactivation to recovery to pre-flare steroid dose will be calculated in study days as: date of clinically significant disease reactivation – date of return to pre-flare steroid dose.

If a subject does not return to their pre-flare steroid dose prior to the end of their study participation, or if the subject does not have in increase in steroid dose due to their flare, then the variable will equal the duration of follow-up for that subject. Appropriate censor variables will be defined to indicate whether the time-to variable represents an event time or a censor time.

**Analysis**: Kaplan-Meier curves will be created for each treatment arm and will include 95% confidence intervals based on the Greenwood method.

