# **Endpoint:**

For each subject, a yes/no variable will be assigned to indicate whether a subject has met the primary endpoint of clinically significant disease reactivation between Day 0 and Week 60, as defined above.

Subjects who terminate early from the study, and who had not previously met primary endpoint, will be handled as follows:

- 1. Subjects who do not have a mild/moderate or severe SELENA-SLEDAI flare at their last study visit will be categorized as not experiencing clinically significant disease reactivation.
- 2. Subjects who have a mild/moderate or severe SELENA-SLEDAI flare at their last study visit:
  - a. Subjects will be categorized as experiencing clinically significant disease reactivation for the following three scenarios:
    - i. Subject has a SELENA-SLEDAI mild/moderate or severe flare at the time of early termination, and a steroid increase/burst to ≥ 15 mg/day prednisone that is sustained through end of study.
    - Subject previously experienced a flare requiring either intraarticular, intra-muscular or IV steroids, or an increase/burst of steroids that was successfully tapered to < 15 mg/day within four

Version: 1.0 Page 18 of 48

<sup>1 For ALE06, prednisone > 0.5 mg/kg/day is categorized as a severe SELENA-SLEDAI flare if the duration is >2 weeks. Increases in prednisone >0.5 mg/kg/day but for ≤2 weeks will be categorized as mild/moderate SELENA-SLEDAI flares.

weeks, and is experiencing a severe flare at the time of early termination.

- iii. Subject has a SELENA-SLEDAI severe flare based on the following clinical components: SLEDAI score; New/Worse disease, and Increase in PhGA without considering prednisone or other treatments
- b. Subjects experiencing flare at the time of early termination, but who do not met the criteria in 2.a. above, will be classified as not experiencing clinically significant disease reactivation.

These cases will be re-categorized under sensitivity analyses for the primary endpoint (see 7.2.3).

The time of clinically significant disease reactivation is defined as the date of the first SELENA-SLEDAI assessment that meets (or goes on to meet) the criteria for clinically significant SLE reactivation. The time-to-event will be defined as the interval: date of disease reactivation – date of Day 0 visit. Subjects who do not experience clinically significant disease will be censored at the last visit date on study.

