#### 7.3.3. Time to First SELENA-SLEDAI Flare

**Endpoint**: The SELENA-SLEDAI instrument will be completed at baseline and every follow-up visit during the course of the 60 week study period for all subjects. The SELENA-SLEDAI assesses flares based on changes in the SLEDAI score, the Physician's Global Assessment (PGA), medication use (prednisone, NSAIDS, Plaquenil, major immunosuppressives), other disease activity criteria, and hospitalization due to SLE. See Section 7.2.1., *Computation of the Primary Endpoint*, for more information on scoring of the SELENA-SLEDAI flare assessment.

For each subject, time from Day 0 to first SELENA-SLEDAI flare and time to first severe SELENA-SLEDAI flare will be calculated in study days as: date of first flare – date of Day 0 visit. Subjects who do not experience SELENA-SLEDAI flare will be censored at their last visit date on study.

**Analysis**: Analyses analogous to those specified in Section 7.3.1, *Time to Clinically Significant Disease Reactivation*, will be performed for time to SELENA-SLEDAI flare. Additionally, sensitivity analysis may be run to assess the impact of new or increased major immunosuppressives as the only cause of severe flare. Subjects who re-start or increase major immunosuppressives, but have no other disease activity that would categorize them as having a severe flare, will be categorized as not having a severe SELENA-SLEDAI flare (i.e. categorized as a mild/moderate flare) and analyses would be replicated using this definition of a severe flare.

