# 7.3.13.1. Time from clinically significant disease reactivation to improvement in BILAG from maximum level during flare

**Endpoint:** See Section 7.2.1, *Computation of the Primary Endpoint*, for details on the definition of clinically significant SLE reactivation, and Section 7.3.4, *Probability of Experiencing a BILAG A Flare*, for more information on the BILAG and its scoring.

For each subject who experiences disease reactivation, time from clinically significant disease reactivation to improvement in BILAG from maximum level (at least an A or B) during the flare will be calculated in study days as: date of clinically significant disease reactivation – date of BILAG improvement. If multiple body systems have a BILAG flare at the visit, then the body system with the most severe score will be tracked for improvement; if multiple body systems have the same score (at least an A or B), then just one needs to show improvement.

Subjects who do not experience improvement in the BILAG prior to the end of their study participation or if the subject doesn't experience an increase in their BILAG score to a B or higher will be censored at their last visit date on study.

**Analysis**: Kaplan-Meier curves will be created for each treatment arm and will include 95% confidence intervals based on the Greenwood method.

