# 7.3.13.2. Time from clinically significant disease reactivation to recovery to baseline BILAG scores or BILAG C, whichever is worse

**Endpoint:** See Section 7.2.1, *Computation of the Primary Endpoint*, for details on the definition of clinically significant SLE reactivation, and Section 7.3.4, *Probability of Experiencing a BILAG A Flare*, for more information on the BILAG and its scoring.

For each subject who experiences disease reactivation, time from clinically significant disease reactivation to recovery to baseline BILAG scores or BILAG C, whichever is worse, will be calculated in study days as: date of clinically significant disease reactivation – date of BILAG recovery.

If a subject does not recover to their baseline BILAG score or BILAG C, whichever is worse, prior to the end of their study participation, or if the subject doesn't experience an increase in their BILAG score, then their BILAG score will be censored at their last visit date on study.

**Analysis**: Kaplan-Meier curves will be created for each treatment arm and will include 95% confidence intervals based on the Greenwood method.

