#### 8.2. Extent of Exposure

Extent of exposure during the trial will be described for MMF. Exposure will be measured as the total number of days on medication defined as last dose date – first dose date + 1 and the cumulative dose of that medication defined as the sum of the doses in mg taken up to the relevant cutoff date. Exposure will be summarized until a subject stops taking study provided MMF.

Version: 1.0 Page 30 of 48

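### SAP 7.3.13: three recovery times are subtracted backwards, and 7.3.13.4 does not say where the follow-up used for censoring starts

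*SAP*

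**What the plan says.** Three of the four recovery endpoints in SAP 7.3.13 are times that start at reactivation and are analysed by Kaplan-Meier in each arm. Their formulas are:

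- 7.3.13.1: "date of clinically significant disease reactivation – date of BILAG improvement"
- 7.3.13.2: "date of clinically significant disease reactivation – date of BILAG recovery"
- 7.3.13.4: "date of clinically significant disease reactivation – date of return to pre-flare steroid dose"

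Elsewhere the SAP subtracts the earlier date from the later one. Time to reactivation (7.2.1, repeated in 7.3.1) is "date of disease reactivation – date of Day 0 visit", time to first flare (7.3.3) is "date of first flare – date of Day 0 visit", and exposure (8.2) is "last dose date – first dose date + 1".

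The censoring rules also differ. 7.3.13.1 and 7.3.13.2 censor at the last visit date. 7.3.13.4 assigns a duration instead. For a subject still above the pre-flare dose when participation ends, it states: "then the variable will equal the duration of follow-up for that subject". Subjects whose steroids were never raised for the flare get the same value. The sentence that follows provides for an event/censor flag and does not give a time origin.

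SAP section 12, which lists changes from the protocol, mentions none of this. Protocol 8.3.2.2 warns that reactivations near the end of follow-up will be censored and that this may be informative. It does not address the formulas.

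**The concern.** There are two separate faults.

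**Sign.** Recovery cannot come before reactivation, so the printed subtraction gives a negative time for every later recovery. Kaplan-Meier cannot use negative times.

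**Censoring origin, 7.3.13.4 only.** Event times run from reactivation. If censored subjects are given their whole time on study, the two kinds of time are on different clocks. An unrecovered subject then stays in the risk set for weeks in which no return could have been observed, and the estimated return is too low. The shortfall grows as reactivations come later, so it could differ between arms whose recovery is the same. This fault deserves the closer look because it produces positive, plausible values that no range check would catch.

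**Working it through.** The documents give no expected recovery figure for these endpoints, so there is no planned number to reproduce.

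**1. Sign.** Take reactivation on day 140 and return on day 196. As printed: 140 − 196 = −56 days. By the convention of 7.2.1 and 7.3.3: 196 − 140 = +56 days. The same holds in all three sections.

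**2. Censor time in 7.3.13.4, read as total time on study.** Follow-up is 60 weeks (420 days), and neither subject returns to the pre-flare dose.

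| Reactivation | Time at risk after reactivation | Literal value |
|---|---|---|
| Day 84 | 420 − 84 = 336 days | 420 days |
| Day 364 (Week 52) | 420 − 364 = 56 days (8 weeks) | 420 days (60 weeks) |

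**3. Effect on the curve.** Assumptions not in the documents: return time T is exponential with mean 16 weeks; everyone is followed to Week 60; reactivation is uniform over a stated window; every subject has a steroid increase; event signs are corrected.

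Let G(v) = 1 − exp(−v/16). The true 24-week return is G(24) = 1 − exp(−1.5) = 0.777.

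Under the literal rule every unrecovered subject is censored at 60 weeks, so nobody is censored before week 24. The 24-week estimate is then the share of subjects seen to return within 24 weeks. Let V = 60 − reactivation week, uniform from L to H. For L < 24 < H:

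estimate = [(24 − L) − 16(exp(−L/16) − exp(−1.5)) + (H − 24) × 0.7769] / (H − L)

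| Reactivation weeks | L to H | Calculation | Literal rule |
|---|---|---|---|
| 8-28 | 32 to 52 | all V exceed 24, so G(24) | 0.777 |
| 4-36 | 24 to 56 | all V at least 24, so G(24) | 0.777 |
| 8-40 | 20 to 52 | (2.986 + 28 × 0.7769)/32 | 0.773 |
| 4-58 | 2 to 56 | (11.450 + 32 × 0.7769)/54 | 0.672 |
| 30-58 | 2 to 30 | (11.450 + 6 × 0.7769)/28 | 0.575 |
| 0-60 | 0 to 60 | (11.570 + 36 × 0.7769)/60 | 0.659 |
| 12-60 | 0 to 48 | (11.570 + 24 × 0.7769)/48 | 0.630 |

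Simulation with 200,000 subjects per scenario gives 0.776, 0.673 and 0.576 for Weeks 8-28, 4-58 and 30-58. With censoring at 60 minus the reactivation week it gives 0.776 to 0.778 in all three.

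**4. Arm difference when true recovery is identical.**

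- Separate windows, Weeks 8-28 against 30-58: 0.777 − 0.575 = 0.20.
- Overlapping windows, Weeks 0-60 against 12-60: 0.659 − 0.630 = 0.03, with both arms below 0.777.

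**5. Other recovery speeds.** I compared reactivations on days 28-168 with days 224-419, reading return at 168 days under the literal rule, with assumed medians of 28, 56 and 112 days. The gaps are 0.985 − 0.800 = 0.19, 0.874 − 0.627 = 0.25 and 0.649 − 0.422 = 0.23. The early-window values match the truth (0.984, 0.875, 0.646). If everyone in an arm reactivates on day 140, the literal and correct estimates agree at 56, 84 and 168 days.

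**6. How many subjects this touches.** SAP section 12 reports 8 reactivations in the first 80 subjects. At that rate 120 subjects give 120 × 8/80 = 12, or 6 per arm if split evenly (an assumption). With 6 subjects and no censoring at all, the standard error of a 0.777 proportion is √(0.777 × 0.223/6) = 0.17.

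**The case against.** **The sign is an obvious slip.** The section titles fix where each interval starts and ends, the SAP's other intervals run the right way, and a programmer would notice negative times at once. This stands. A reader might infer that the recovery curves would show no recovery, because negative event times would be dropped and only censored records kept. That would require an analyst to discard every event and report the result, and nothing in the documents suggests it.

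**Follow-up may mean follow-up after reactivation.** The variable being filled is itself a time since reactivation, the sister endpoints censor at the last visit, and Protocol 8.3.2.2 shows that the authors knew late reactivators have little follow-up left. On that reading the censoring is correct. This stands as a reasonable reading, but the SAP does not state it.

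**Dependence on flare timing is narrower than it may look.** A reader might extend it to all three sections. Once the sign is right, last-visit censoring makes 7.3.13.1 and 7.3.13.2 sound in this respect. A reader might also expect a spurious arm difference of about 20 points. That needs reactivation windows that do not overlap, and Protocol 3.1.1 expects most flares early, where the bias is about nil.

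**Stakes are low.** SAP 7.3 calls the secondary analyses exploratory, and sampling error with so few subjects is of the same order as the largest bias shown. This also stands.

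**Correct censoring leaves one matter open.** Subjects with no steroid increase have no raised dose to return from, yet they would still count as not returned. If 20% were such subjects, and 0.875 of the rest returned by 168 days, the curve would read 0.8 × 0.875 = 0.70. This is a separate choice that the correction below does not settle.

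**Conclusion.** The point holds, at minor to moderate severity.

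- **Sign (high confidence).** Three printed formulas are reversed and contradict 7.2.1, 7.3.1, 7.3.3 and 8.2. The likely practical damage is small because the error shows itself.
- **Censoring origin in 7.3.13.4 (moderate confidence).** The text leaves the origin unstated, and its literal sense is total time on study. On that reading, return to the pre-flare dose is understated when reactivations are late or widely spread. With an exponential return time of mean 16 weeks, the 24-week estimate ranges from about 0.78 (no bias, Weeks 8-28) through 0.67 (Weeks 4-58) to 0.58 (Weeks 30-58). These figures illustrate direction and possible size. They do not predict this trial's results, and overlapping arms would differ by only a few points.

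The primary endpoint and time to reactivation are not affected.

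**What to change.** 1. In SAP 7.3.13.1, 7.3.13.2 and 7.3.13.4, define the time as the date of improvement, recovery or return minus the date of reactivation.
2. In 7.3.13.4, replace the follow-up duration with a censor time equal to the last visit date minus the reactivation date. This matches the last-visit censoring in 7.3.13.1 and 7.3.13.2.
3. While editing 7.3.13.4, state whether subjects with no steroid increase belong in this analysis.

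Items 1 and 2 cost a few words of SAP text and about one line of code per endpoint. They need no new data and no change of method.

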# 7.4. Secondary Mechanistic Endpoints

#### 7.4.1. C3, C4, and anti-dsDNA Levels

**Endpoint**: C3, C4, and anti-dsDNA are run at baseline and every follow-up visit, including any Flare or Endpoint visits, during the course of the 60 week study period and run by a central laboratory.

Specifically, levels of C3, C4, and anti-dsDNA at Baseline, Week 20, at the time of first flare, and immediately prior to first flare will be analyzed.

**Analysis**: Descriptive statistics (mean, standard deviation, median, minimum, maximum and number of subjects in a group) will be computed by treatment group and separately for subjects who do/do not experience clinically significant disease reactivation at each specified time point. Summary statistics will be plotted versus time at the relevant time points. Plots for individual subjects will also be created.

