### 2.2.3 Secondary Mechanistic Objectives

• To identify baseline autoantibody, cytokine/chemokine, and gene expression characteristics that are associated with an increased risk of SLE flare.

- To identify autoantibody, cytokine/chemokine, and gene expression characteristics present at Week 20 or changes in those characteristics from baseline to Week 20 that are associated with an increased risk of flare.
- To identify autoantibody, cytokine/chemokine and gene expression changes associated with withdrawal of MMF apart from flare.

Markers of particular interest include:

- Serologic markers: dsDNA antibodies, C3 levels, C4 levels, and antibodies toward Sm, ribonucleoprotein (RNP), SSA/Ro, & SSB/La;
- Presence/absence of a "B cell fingerprint" assessed by gene expression profiling;
- $\circ$  Presence/absence of an "Interferon- $\alpha$  biosignature" assessed by gene expression profiling;
- Levels of cytokines or chemokines associated with the interferon- $\alpha$  and  $\gamma$  pathway (measured by bead based assays or ELISA).

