#### 6.3.1 Serologic Markers

Serum for serologic markers including C3, C4, and antibodies to dsDNA, Sm, RNP, SSA/Ro and SSB/La will be collected at every scheduled visit and every Flare Visit.

C3, C4, and dsDNA antibodies (anti-dsDNA) are needed at each visit as part of the SELENA-SLEDAI\* scoring system, but will also be analyzed as independent markers to define the utility of the markers in predicting which subjects will meet the primary endpoint of clinical disease activation.

Antibodies to Sm, RNP, SSA/Ro, and SSB/La will be measured from a serum specimen at Baseline and Week 60 for all subjects. To evaluate these markers as predictors of flare, samples collected at pre-flare, flare, and post-flare time points may be analyzed for those subjects who flare. For subjects who do not flare, samples may be analyzed at three additional time points for comparison to the results for flaring subjects.

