#### 6.3.3 **Transcript Profiling Studies**

RNA for transcript analysis will be collected at every scheduled visit and every Flare Visit and stored until the study is completed.

Hypotheses:

- i. Subjects with an "Immunologically Active B Cell Fingerprint" will be more likely to flare than subjects with an "Inactive B Cell Fingerprint";
- ii. Subjects with an "Interferon- $\alpha$  Signature" will be more likely to flare than subjects who lack an Interferon- $\alpha$  Signature.

Transcript profiling for gene expression will be performed on the subset of subjects who flare (estimated at ~15) and matched subjects who do not flare (estimated at 30). For flaring subjects, RNA transcripts will be analyzed at each of 5 time points (Baseline, Week 20, first flare, and the time points immediately prior to and after first flare). For the subjects who do not flare, RNA transcripts will be analyzed at Baseline, Week 20, and time points comparable to the pre-flare, flare, and post-flare time points for matched flaring subjects. All samples will be analyzed at the end of the study, after all flares have been identified. Differences in gene expression at Baseline will be explored among subjects who do and do not flare. In addition, differences in gene expression among treatment arms will also be investigated.

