# 7.4.2. Changes in C3, C4, and anti-dsDNA Levels

**Endpoint**: C3, C4, and anti-dsDNA are run at baseline and every follow-up visit, including any Flare or Endpoint visits, during the course of the 60 week study period and run by a central laboratory. Change from baseline will be calculated for each test and time point.

Specifically, change from baseline in levels of C3, C4, and anti-dsDNA at Week 20, the time of first flare, and immediately prior to first flare will be analyzed.

Version: 1.0 Page 29 of 48

**Analysis**: Descriptive statistics (mean, standard deviation, median, minimum, maximum and number of subjects in a group) will be computed by treatment group and separately for subjects who do/do not experience clinically significant disease reactivation at each specified time point. Summary statistics will be plotted versus time at the relevant time points. Plots for individual subjects will also be created.

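### Serology at first flare and at the visit before it has no flare-free comparator at the same visit, so any drift after MMF withdrawal would be mixed with the approach of flare in those rows

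*SAP*

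**What the plan says.** SAP 7.4.1 takes levels of the three markers "at Baseline, Week 20, at the time of first flare, and immediately prior to first flare will be analyzed". SAP 7.4.2 takes "change from baseline in levels of C3, C4, and anti-dsDNA at Week 20, the time of first flare, and immediately prior to first flare". Both sections give descriptive statistics by treatment group and "separately for subjects who do/do not experience clinically significant disease reactivation at each specified time point", with summary plots and plots for individual subjects. No test or confidence interval is planned. Protocol 8.3.3 uses the same two groupings. None of these sections gives an index visit to a subject who does not flare.

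The data for a comparator exist: "C3, C4, and anti-dsDNA are run at baseline and every follow-up visit, including any Flare or Endpoint visits".

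Protocol 6.3.1 says that C3, C4 and anti-dsDNA will be analysed as independent markers "to define the utility of the markers in predicting which subjects will meet the primary endpoint of clinical disease activation". Protocol 2.2.3 has three mechanistic objectives. The first two concern Baseline characteristics, and Week 20 characteristics or changes, that are associated with flare risk. The third is "To identify autoantibody, cytokine/chemokine and gene expression changes associated with withdrawal of MMF apart from flare". Protocol 2.2.3 lists dsDNA antibodies, C3 and C4 among the markers of particular interest.

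For other assays the protocol provides for subjects who do not flare:

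- transcripts (6.3.3) are analysed in them at "time points comparable to the pre-flare, flare, and post-flare time points for matched flaring subjects";
- cytokines (6.3.2) are analysed at three additional time points, not stated to be matched;
- Sm, RNP, Ro and La antibodies (6.3.1) may be analysed at three additional time points.

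**The concern.** Two of the four time points are defined by an event that many subjects will not have. Reactivation requires a flare plus a sustained increase in therapy, so at those time points the no-reactivation column can hold only subjects who flared without meeting the therapy criteria. SAP 7.4.1 does not say whether first flare means any SELENA-SLEDAI flare or reactivation; under the second meaning that column is empty. Crossing arm with reactivation status would not help, because a never-flaring subject still has no value to enter.

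A withdrawal-arm subject who flares at Week 32 has been off MMF since Week 12. The change from Day 0 to Week 24 in that subject contains whatever stopping MMF does to complement and anti-dsDNA in everyone, plus whatever is specific to a coming flare. Only subjects of the same arm at the same week who have not flared can separate the two. At stake is how far the pre-flare row can support the predictive aim of Protocol 6.3.1.

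**Working it through.** **No plan figure to reproduce.** The point concerns the comparison set, and the plan states no number for it. The nearest figure is the roughly 15 flaring subjects in Protocol 6.3.3. With 60 per arm and the risks considered in Protocol 8.1, 60 × 0.10 + 60 × 0.15 = 15 and 60 × 0.05 + 60 × 0.20 = 15. The range is 60 × 0.05 + 60 × 0.10 = 9 to 60 × 0.15 + 60 × 0.30 = 27. The protocol does not say how it reached 15.

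**Who can appear in each row**

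| Row | Flared, reactivation | Flared, no reactivation | Never flared |
|---|---|---|---|
| Baseline | yes | yes | yes |
| Week 20 | yes | yes | yes |
| Visit before first flare | yes | yes (none if first flare means reactivation) | no |
| First flare | yes | yes (none if first flare means reactivation) | no |

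**Size under an assumed drift.** Inputs:

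- Visits at Weeks 0, 4, 8, 12, 16, 20, 24, 32, 40, 48 and 60 (Protocol 3.1).
- Assumption: the marker falls by d = 0.05 to 0.10 SD per 4 weeks from Week 4 and levels off at Week 24. That is 0 steps to Week 4, then 1, 2, 3, 4 and 5 steps at Weeks 8, 12, 16, 20 and 24, and 5 steps afterwards.
- Assumption: 40% flare by Week 60 at constant hazard, λ = −ln(0.6)/60 = 0.00851 per week, independent of the marker.

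The share of first flares detected at visit b, with preceding visit a, is [exp(−λa) − exp(−λb)]/0.4:

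| Flare visit | 4 | 8 | 12 | 16 | 20 | 24 | 32 | 40 | 48 | 60 |
|---|---|---|---|---|---|---|---|---|---|---|
| Share | 0.084 | 0.081 | 0.078 | 0.076 | 0.073 | 0.071 | 0.134 | 0.125 | 0.117 | 0.161 |
| Steps at preceding visit | 0 | 0 | 1 | 2 | 3 | 4 | 5 | 5 | 5 | 5 |
| Steps at flare visit | 0 | 1 | 2 | 3 | 4 | 5 | 5 | 5 | 5 | 5 |

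The weighted means are 3.42 steps before flare and 3.80 at flare. Multiplied by d:

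- pre-flare change: 3.42 × 0.05 = 0.17 to 3.42 × 0.10 = 0.34 SD, downward;
- at-flare change: 3.80 × 0.05 = 0.19 to 3.80 × 0.10 = 0.38 SD, downward.

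All of this is drift. Flare-free subjects of the same arm have the same expected value at the same visit, so the expected difference is 0.

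**Simulation with the comparator added.** Sixty withdrawal-arm subjects, no marker-flare link, within-subject correlation 0.5 (assumed), linear drift from Day 0 to Week 20 and then flat, 60-week flare risk 0.15 to 0.50 (assumed). Flares whose preceding visit is Day 0 were left out.

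| Drift by Week 20 (SD) | Mean pre-flare change in flaring subjects (SD) | Difference from same-arm, same-visit flare-free subjects (SD) |
|---|---|---|
| 0 | about 0 | −0.01 to 0.01 |
| 0.25 | 0.20 to 0.22 | −0.01 to 0.00 |
| 0.5 | 0.41 to 0.42 | −0.01 to 0.01 |
| 1.0 | 0.81 to 0.86 | −0.01 to 0.01 |

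**Flares at Week 4.** Their preceding scheduled visit is Day 0, so the pre-flare change in SAP 7.4.2 is zero by construction. Their share of first flares is [1 − exp(−4λ)]/p. For p = 0.2, 0.4 and 0.6 this is 7.4%, 8.4% and 9.9% at constant hazard, and 10.5%, 11.9% and 13.9% if the hazard is doubled up to Week 24. Unscheduled Flare visits are ignored.

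**Serology in the flare index.** Low complement scores 2 and raised DNA binding scores 2 (SAP 14.3). Together 2 + 2 = 4, and a SLEDAI change above 3 already counts as a mild or moderate flare.

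**The case against.** A reader might infer that a general drift will be mistaken for a warning sign of flare, and that the mechanistic objectives go unanswered. The documents do not support that.

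- **Drift may be visible anyway.** SAP 7.4.2 reports the Week 20 change by arm, with flare-free subjects included. Under the drift assumed above, that row shows four steps in the withdrawal arm: 4 × 0.05 = 0.20 to 4 × 0.10 = 0.40 SD, at least as large as the pre-flare 0.17 to 0.34 SD. Individual plots are planned, and flaring maintenance-arm subjects appear at the same anchors. A careful reader could suspect drift. This stands, but none of these is a same-arm, same-visit reference, and Week 20 does not match flares at other visits.
- **The objectives name other time points.** The risk-marker objectives in Protocol 2.2.3 name Baseline and Week 20, where flare-free subjects are present, and the objective on withdrawal apart from flare names no flare-anchored visit. The explicit hypothesis about the visit before flare, in Protocol 6.3.2, concerns interferon-associated cytokines and chemokines. This stands; what remains is the general predictive aim of Protocol 6.3.1.
- **The tables are a descriptive first step.** Protocol 8.3.3 says its summaries are not exhaustive and precede any modelling. This stands and lowers the priority.
- **The transcript contrast is imperfect.** Matching in Protocol 6.3.3 selects stored samples to assay, whereas serology is run on everyone. That explains the difference, but it also means a serology comparator needs no new assays.
- **The zeros at Week 4 are minor.** They pull the pre-flare mean towards no change, and Day 0 is a genuine last observation before flare. This stands, so excluding them is a preference.
- **Drift size and flare share are assumed.** This stands. The gap in the comparison does not depend on them; its consequence does.

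**Conclusion.** The point holds in conditional form. The two flare-anchored rows contain only subjects who flare, and the reactivation split cannot supply a flare-free comparator. If C3, C4 or anti-dsDNA drift after withdrawal, those rows mix time off MMF with approach of flare. Under the assumed drift and flare pattern, a marker unrelated to flare shows a pre-flare change of 0.17 to 0.34 SD; with no drift it shows none.

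The effect is confined to the predictive reading of these two time points. The Baseline and Week 20 objectives and the primary result are unaffected. At-flare values are also partly abnormal by definition because serology scores in the SLEDAI. A flare-free reference does not remove that, so the pre-flare row is the more informative one. This is an inexpensive improvement to an exploratory table, best specified before the data are examined.

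**What to change.** Add to SAP 7.4.1 and 7.4.2:

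- State whether first flare means any SELENA-SLEDAI flare or reactivation.
- For each first flare at visit v, form a reference from all subjects in the same arm who are still in follow-up and flare-free through v. Use their values at v and at the preceding visit; if the flare visit is unscheduled, use the nearest scheduled visit.
- Show levels and changes in flaring subjects alongside this reference and as differences from it.
- Report how many subjects have Day 0 as their pre-flare visit. Leaving them out of the pre-flare change row is optional.
- Note beside the at-flare row that complement and DNA binding contribute to the SLEDAI score.

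The cost is a few sentences and modest programming, with no new samples, assays or visits. The downside is a somewhat more complex exploratory table.
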